10.4.8 Exploratory Endpoint: Chemo-Free Interval

The chemo-free interval will be calculated in months as the time since the last dose of the most recent chemotherapy regimen to the date of the first dose of a subsequent chemotherapy after study drug + 1 day. Patients without a documented start of a subsequent chemotherapy after study drug will be censored on the date of their last available assessment.

The same statistical test used for the primary endpoint (i.e., stratified log rank test and a stratified Cox proportional model) will be used to compare rucaparib to placebo for this endpoint.

10.4.9 Exploratory Endpoint: Time to Start of First Subsequent Anti-cancer Treatment

The time to start of the first subsequent anti-cancer treatment will be calculated in months as the time from randomization to the date of the first dose of the first subsequent anti-cancer treatment regimen after study drug + 1 day. Patients without a documented start of a subsequent anti-cancer treatment after study drug will be censored on the date of their last available assessment.

The same statistical test used for the primary endpoint (i.e., stratified log rank test and a stratified Cox proportional model) will be used to compare rucaparib to placebo for this endpoint.

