## **11.3 Interim Analysis**

No formal interim efficacy analyses will be performed.

All endpoints were summarized at the time the primary endpoint (invPFS) was unblinded in April 2017; however, the following efficacy endpoints are still being collected and will be summarized at the time of the study closing:

- Secondary Endpoint of Final OS
- Post-progression exploratory endpoints (PFS2, time to first subsequent anticancer treatment, time to second subsequent anticancer treatment, and chemotherapy-free interval)

The OS data were heavily censored at the time of the primary endpoint analysis. In order to adjust for multiple analyses of OS at a later stage, a stopping rule will be applied. The Haybittle-Peto stopping rule will be applied, where an OS result with a p-value < 0.001 can be used to claim superiority of rucaparib compared to placebo. This means that a p-value < 0.05 can be utilized at the final analysis, which is projected to occur once 70% of the death events have been collected.

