10 EFFICACY ANALYSIS

10.1 Primary Efficacy Analysis

The primary efficacy endpoint is PFS as assessed by the investigator (invPFS). The time to invPFS will be calculated in months as the time from randomization to disease progression +1 day, as determined by RECIST v1.1 criteria² or death due to any cause, whichever occurs first.

Only scans and deaths prior to the start of any subsequent anti-cancer treatment or within 90 days of treatment end date will be included in the analysis. Patients without a documented event of progression will be censored on the date of their last tumor assessment (i.e., radiologic assessment) prior to the start of any subsequent anti-cancer treatment or within 90 days of treatment end date. Patients who withdrew without a disease progression event and do not have any post-baseline tumor assessment will be censored at date of randomization.

The stratified log rank test will be considered the primary analysis for invPFS comparing rucparib to placebo. In addition, a stratified Cox proportional hazard model will be used to calculate the hazard ratio (HR) between the treatment groups. The following randomization strata are used to estimate the treatment effect:

- HRD classification by the CTA (tBRCA, nbHRD, biomarker negative)
- Best response to most recent platinum-based regimen (CR, PR)
- Interval between completion of the penultimate platinum-based regimen and disease progression (6 to 12 months or > 12 months)

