10.4.10 Exploratory Endpoint: Time to Start of Second Subsequent Anti-cancer Treatment

The time to start of the second subsequent anti-cancer treatment will be calculated in months as the time from randomization to the date of the first dose of the second subsequent anti-cancer treatment regimen after study drug + 1 day. Patients without a documented start of a second subsequent anti-cancer treatment after study drug will be censored on the date of their last available assessment.

The same statistical test used for the primary endpoint (i.e., stratified log rank test and a stratified Cox proportional model) will be used to compare rucaparib to placebo for this endpoint.

10.4.11 Exposure- Response PK Report: Rucaparib PK, invPFS, irrPFS, CA-125, AEs, Clinical Laboratory Abnormalities, and Dose Modifications

An Exposure-Response PK analysis will be performed and documented in a separate report.

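### SAP 10.4.8 to 10.4.10 censor deaths that occur before the next therapy, so the planned Kaplan-Meier times overstate time alive without further treatment

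*SAP*

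**What the plan says.** SAP 10.4.9 measures from randomization to the first dose of the first subsequent regimen and adds: "Patients without a documented start of a subsequent anti-cancer treatment after study drug will be censored on the date of their last available assessment". SAP 10.4.10 has the parallel sentence for the second regimen: "Patients without a documented start of a second subsequent anti-cancer treatment after study drug will be censored on the date of their last available assessment". SAP 10.4.8, which starts from the last dose of the most recent chemotherapy, has it for chemotherapy: "Patients without a documented start of a subsequent chemotherapy after study drug will be censored on the date of their last available assessment". None of the three sections mentions death.

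Each endpoint is compared by stratified log-rank test and stratified Cox model. SAP 3 summarizes time-to-event variables by Kaplan-Meier, with quartiles and event rates every 6 months where estimable.

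Elsewhere the SAP counts death. In SAP 10.1 invPFS ends at progression "or death due to any cause, whichever occurs first". SAP 10.2.3 (irrPFS) and 10.4.2 (PFS2) also include death from any cause.

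Protocol 11.3 lists the three endpoints beside PFS2 as still being collected and to be summarized at study close, but gives no event or censoring rule. SAP 10.4 makes no multiplicity adjustment for exploratory endpoints.

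**The concern.** A patient who dies without the next therapy can never start it. The rule nevertheless treats her like a patient who is alive, untreated and may start later, and it censors her at an assessment that can precede her death. A Kaplan-Meier curve built this way describes a setting in which nobody dies before treatment. Its median will naturally be read as the time patients spent alive without further treatment, and it is longer than that.

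The SAP is also inconsistent. PFS2 belongs to the same post-progression set, so one report would treat the same death as an event in one endpoint and as censoring in its neighbours. By study close more deaths will have accrued than at the primary analysis. Time to second subsequent treatment is the most exposed, because death can come before either line.

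**Working it through.** **Inputs.** The event rules come from SAP 10.4.8 to 10.4.10. The plan states no figure for these endpoints, so the invPFS design values in SAP 2.3 are borrowed for scale only: HR 0.50, 0.60 and 0.70; medians 6 v 12, 6 v 10 and 6 v 8.5 months; 2:1 allocation. The share d is an assumption throughout.

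**Step 1: check of the borrowed design row.** For ITT, events needed = (1.960 + 1.282)² / [(2/3)(1/3)(ln 0.70)²] = 10.51 / (0.2222 × 0.1272) = 372. The planned 378 give 90.5% power against the stated 90%, so the row is reproduced. This confirms the inputs only.

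**Step 2: medians, constant hazards.** Let h be the hazard of starting therapy and m the hazard of untreated death, so d = m/(h + m). The death-censored median is ln 2 / h and the therapy-or-death median is ln 2 / (h + m). Their ratio is (h + m)/h = 1/(1 - d).

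| d | Excess of death-censored median | A death-censored 12 months becomes |
|---|---|---|
| 5% | 5% | 12 × 0.95 = 11.4 |
| 10% | 11% | 12 × 0.90 = 10.8 |
| 20% | 25% | 12 × 0.80 = 9.6 |

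The excess arises even when d is the same in both arms. Censoring is taken at death; moving it back to the last assessment is not modelled.

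**Step 3: hazard ratio, constant hazards.** HR(therapy or death) = HR(death-censored) × (1 - d_placebo)/(1 - d_rucaparib).

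| Death-censored HR | Equal d | d 5% placebo, 10% rucaparib | d 10% placebo, 5% rucaparib |
|---|---|---|---|
| 0.50 | 0.50 | 0.53 | 0.47 |
| 0.60 | 0.60 | 0.63 | 0.57 |
| 0.70 | 0.70 | 0.74 | 0.66 |

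Equal d means equal shares of endings, not equal mortality. With the same death hazard in both arms, d_placebo = 5% and HR 0.70, set the placebo start hazard to 1. Then m = 0.05/0.95 = 0.0526, d_rucaparib = 0.0526/0.7526 = 7.0%, and the therapy-or-death HR is 0.7526/1.0526 = 0.715.

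**Step 4: second subsequent treatment.** This is a two-stage exponential simulation with 200,000 patients per arm, an assumed 10-month median from first to second therapy, and uniform censoring over 12 to 60 months. Shares are placebo/rucaparib.

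| First-therapy medians | d before first | d before second | HR, death-censored to therapy-or-death | Rucaparib median (months) |
|---|---|---|---|---|
| 6 v 12 | 5%/5% | 20%/20% | 0.60 to 0.61 | 27.6 to 22.8 |
| 6 v 8.5 | 2%/10% | 20%/30% | 0.77 to 0.98 | 23.3 to 16.7 |
| 6 v 8.5 | 10%/2% | 30%/20% | 0.79 to 0.64 | 23.1 to 19.5 |

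**Step 5: death and therapy linked through prognosis.** Take a shared gamma frailty (mean 1, shape 2), start hazard 0.03 per month and death hazard 0.015, so d = 33%.

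- No deaths: (1 + 0.015t)^(-2) = 0.5 gives t = 27.6 months.
- Therapy or death: (1 + 0.0225t)^(-2) = 0.5 gives 18.4 months.
- Death-censored Kaplan-Meier: (1 + 0.0225t)^(-4/3) = 0.5 gives 30.3 months.

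The factor 27.6/18.4 = 1.50 = 1/(1 - d) comes from what is being measured. The further 30.3/27.6 = 1.10 is bias from informative censoring. With start hazard 0.06 and d = 8%, the medians are only 14.0 v 12.7 months.

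**The case against.** The strongest reply is that time to start of therapy and time to therapy or death are different estimands. The HR obtained by censoring deaths is a legitimate cause-specific HR, and Step 5 shows that most of the median gap comes from the change of definition. That stands. It does not rescue the Kaplan-Meier median as a measure of treatment-free time, and the SAP neither states the cause-specific reading nor says how deaths are handled.

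The consequence is also small. The three endpoints are exploratory and outside the step-down procedure, and no confirmatory test, sample size or stopping rule depends on them. Deaths remain visible in OS and PFS2. This stands too and limits the weight of the point.

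A reader might go further and infer that the rule can reverse the arm comparison, or that it favours rucaparib. The documents do not support either. From Step 3, a therapy-or-death HR above 1 needs d_rucaparib > 1 - HR × (1 - d_placebo). With no untreated deaths on placebo, that is more than 50%, 40% or 30% of rucaparib endings at HR 0.50, 0.60 or 0.70. Reversal is easier if the effect on starting therapy is near null, or in second therapy with a large imbalance (0%/30% before first and 20%/50% before second moves 0.54 to 1.26), but nothing in the documents points to such figures. Simulating the Step 5 frailty with no effect on starting therapy, and the death hazard doubled on rucaparib from 0.01 to 0.02, gives about 0.95 death-censored and about 1.19 for therapy or death. The first is close to the true cause-specific value of 1; the second carries the assumed excess mortality. If untreated deaths were commoner on placebo, censoring them would understate the rucaparib benefit.

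**Conclusion.** The point holds for the Kaplan-Meier summaries. Followed as written, all three sections censor untreated deaths and give medians and event rates that overstate time alive without further treatment, by a factor 1/(1 - d) under constant hazards and somewhat more if poor prognosis drives both death and therapy. The HR is a valid cause-specific quantity. For first therapy under constant hazards it equals the therapy-or-death HR when d is equal between arms; otherwise the two differ in either direction, most plausibly for second subsequent treatment. No reversal is shown.

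The reading of the text is firm. The size is not, because neither document gives a rate of death before therapy in either arm. The conclusion also assumes that the SAP definitions carry over to the closing analysis, since Protocol 11.3 supplies none. As the endpoints are exploratory, this is a correction worth making and not a threat to the trial's main conclusions.

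**What to change.** In SAP 10.4.8, 10.4.9 and 10.4.10, define the event as start of the stated therapy or death from any cause, whichever is first, in line with PFS2. Report the number of deaths before therapy by arm for each endpoint. If time to therapy alone is kept, replace the Kaplan-Meier curve with cumulative incidence treating death as a competing event, and label the Cox result as cause-specific.

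No new data are needed. Protocol 5.1.5 follows survival and subsequent treatments together about every 12 weeks, and Protocol 13.6 keeps the death and subsequent-therapy forms in use after Amendment 5. The cost is SAP wording and a little extra analysis of exploratory endpoints. The reported times will be shorter than under the present rule.

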10.4.10 Exploratory Endpoint: Time to Start of Second Subsequent Anti-cancer Treatment

The time to start of the second subsequent anti-cancer treatment will be calculated in months as the time from randomization to the date of the first dose of the second subsequent anti-cancer treatment regimen after study drug + 1 day. Patients without a documented start of a second subsequent anti-cancer treatment after study drug will be censored on the date of their last available assessment.

The same statistical test used for the primary endpoint (i.e., stratified log rank test and a stratified Cox proportional model) will be used to compare rucaparib to placebo for this endpoint.

10.4.11 Exposure- Response PK Report: Rucaparib PK, invPFS, irrPFS, CA-125, AEs, Clinical Laboratory Abnormalities, and Dose Modifications

An Exposure-Response PK analysis will be performed and documented in a separate report.

11 STATISTICAL / ANALYTICAL ISSUES

11.1 Statistical Hypothesis

The primary statistical hypothesis for this study is to test for differences in PFS within each of the nested populations (tBRCA, HRD and ITT) using a stratified log-rank test.

H0: HR (rucaparib/placebo) \geq 1. Ha: HR (rucaparib /placebo) < 1.

Stratification factors include:

- HRD classification tBRCA or nbHRD or biomarker negative) as determined by CTA
- Interval between completion of the penultimate platinum-based regimen and disease progression (6 to 12 months or >12 months)
- Best response (RECIST CR or PR [RECIST and/or GCIG CA-125] response) to platinum regimen received immediately prior to initiation of rucaparib maintenance therapy

All efficacy analyses will be based on the randomization strata given at randomization, however, a sensitivity analysis of invPFS may be performed using the actual strata if patients have been allocated incorrectly.

11.2 Handling of Dropouts or Missing Data

[figure not shown]
All patients with a deleterious tBRCA mutation based on the CTA will be included in the HRD positive subgroup even if the percent of genomic LOH is unknown. Patients without a deleterious tBRCA mutation and without a genomic LOH result will only be included in the analyses in the ITT and Safety Populations.

Imputation of missing baseline values for the FOSI-18 will be performed as supportive analyses. For patients without a baseline value, the baseline value will be imputed by using the FOSI-18 assessment performed closest to randomization and may include assessments performed up to and including Cycle 2 Day 1.

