**3.3.2.1.2 Study CO-338-017**

Study CO-338-017 (ARIEL2) is a Phase 2 study of rucaparib as monotherapy treatment for relapsed, platinum-sensitive high-grade ovarian, fallopian tube or primary peritoneal cancer. The purpose of this study is to define a tumor-based molecular signature of HRD in ovarian cancer that correlates with response to rucaparib and enables selection of appropriate ovarian cancer

patients for treatment with rucaparib. The trial is enrolling patients with and without a BRCA1/2 mutation in order to enable identification of this response signature, which will then be prospectively applied to the primary analysis of study CO -338-014 (ARIEL3). Tumor HRD status is assessed using next generation sequencing, with an algorithm for HRD status based on the presence of a BRCA mutation (germline or somatic) and/or degree of tumor genomic LOH, a phenotypic consequence of HRD.

All patients enrolled into Clinical Study CO-338-017 (ARIEL2) must have received at least 1 prior platinum-based treatment regimen, received a platinum-based regimen as their last course of treatment and have platinum-sensitive disease, defined as disease progression >6 months after the last dose of platinum. In addition, all patients must have disease that can be biopsied and is measurable by RECIST v1.1. Rucaparib 600 mg BID is administered continuously until disease progression.

Clinical Study CO-338-017 (ARIEL2) was initiated in October 2013. As of 27 June 2014, 72 of 180 planned patients have been enrolled. The median age is 65.5 years (range 44 – 83) and the majority of patients (n= 54, 75%) had Eastern Cooperative Oncology Group (ECOG) performance status of 0.

The most frequent (reported in  $\geq 15\%$  of patients treatment-related AEs (all grades) as of 27 June 2014 are gastrointestinal-related toxicities (nausea, constipation, vomiting, diarrhea, and abdominal pain), fatigue, elevations in ALT/AST, decreased appetite, and dysgeusia. Transaminase elevations occur early in treatment and are generally transient and resolve or stabilize. All patients who experienced AEs related to rucaparib, including those with Grade 3 transaminase elevation, were successfully managed by treatment interruption and/or a dose reduction. No patient has discontinued rucaparib due to a treatment-related AE. No patients have died on study or within 30 days of last dose of rucaparib.

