3 GENERAL ANALYSIS CONVENTIONS

The summary tables will be presented by randomized treatment group (rucaparib vs placebo) within the nested populations outlined in the step-down procedure in Section 3.2 and other subgroups of interest.

Quantitative variables will typically be summarized using frequencies and percentages for appropriate categorizations and may also be summarized using descriptive statistics. For variables summarized with descriptive statistics, the following will be presented: N, mean, standard deviation, median, minimum, and maximum. Categorical variables will be presented using frequencies and percentages. The Kaplan-Meier methodology will be used to summarize time-to-event variables. If estimable, the 25th, 50th (median), and 75th percentiles will be presented along with the Kaplan-Meier estimates of event rates at 6-month intervals. The number of patients with events and the number of censored patients will also be presented. The stratified log rank test will be used to compare the PFS distributions between the randomized treatment groups. In addition, the Cox proportional hazards model will be used to estimate the hazard ratio between the randomized treatment groups. Months will be calculated as number of days divided by 30.4375.

All data will be used to their maximum possible extent, but without any imputations for missing data.

Unless otherwise indicated, baseline is defined as the last measurement on or prior to randomization.

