10.2.1 Disease Related Symptoms – Physical Subscale of the FOSI-18

The time to an event of worsening in the DRS-P subscale of the FOSI-18 will be defined as the time from randomization to a 4 point reduction in the DRS-P subscale. Patients without a documented event of a 4 point reduction will be censored on the date of their last adequate FOSI-18 assessment or date of randomization if no FOSI-18 assessments have been completed. For patients without a baseline FOSI-18 assessment their values will be censored at date of randomization.

The same statistical test used for the primary endpoint (i.e., stratified log rank test and a stratified Cox proportional model) will be used to compare rucaparib to placebo for this endpoint.

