10.2.2 Total Score of the FOSI-18

The time to an event of worsening in the total score of the FOSI-18 will be defined as the time from randomization to an 8 point reduction in the total score. Patients without a documented event of an 8 point reduction will be censored on the date of their last adequate FOSI-18 assessment or date of randomization if no FOSI-18 assessments have been completed. For patients without a baseline FOSI-18 assessment their values will be censored at date of randomization.

The same statistical test used for the primary endpoint (i.e., stratified log rank test and a stratified Cox proportional model) will be used to compare rucaparib to placebo for this endpoint.

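### The supportive FOSI-18 analyses may take an on-treatment score, as late as Cycle 2 Day 1, as a missing baseline; the effect is probably small and the confirmatory tests are untouched

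*SAP*

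**What the plan says.** SAP 11.2 states: "Imputation of missing baseline values for the FOSI-18 will be performed as supportive analyses". For a patient without a baseline, "the baseline value will be imputed by using the FOSI-18 assessment performed closest to randomization", and the candidates "may include assessments performed up to and including Cycle 2 Day 1". Nothing in that paragraph requires the substitute to precede the first dose.

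The main analyses work differently. SAP 10.2.1 defines the DRS-P event as the "time from randomization to a 4 point reduction in the DRS-P subscale", and SAP 10.2.2 defines the other as the "time from randomization to an 8 point reduction in the total score". Both sections say: "For patients without a baseline FOSI-18 assessment their values will be censored at date of randomization". The general convention in SAP section 3 is to use all data "but without any imputations for missing data", so 11.2 is an exception to it.

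The schedule decides which score is substituted. The protocol collects FOSI-18 within 28 days before randomization (9.2) and on Day 1 of Cycles 1 and 2, before that day's dose (9.3.1). Treatment starts within 3 days of randomization (5.1.2), and cycles last 28 days (5.1.3).

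**The concern.** A baseline should not be able to contain the effect of treatment. The Cycle 1 Day 1 score meets that test because it is taken before any dose. The Cycle 2 Day 1 score does not: it follows about 28 days of dosing, and the instrument's 7-day recall (Protocol Appendix E) lies wholly within that time. A patient whose score has already fallen by then starts from the lower value and needs a further 4 points (DRS-P) or 8 points (total score) to have an event. Time still runs from randomization, so such a patient also has no chance of an event in the first four weeks.

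An early fall on rucaparib is plausible. The DRS-P items cover energy, fatigue, pain, cramps and constipation, and the total score adds nausea, vomiting and bother from side effects. Protocol 3.3.2.1.2 lists among the common treatment-related events "gastrointestinal-related toxicities (nausea, constipation, vomiting, diarrhea, and abdominal pain), fatigue".

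At stake is how far the supportive analysis can be trusted. Patients without a baseline contribute nothing to the main analysis, so the supportive analysis is the only place where they count. If their baselines may already reflect treatment, its agreement with the main result is weaker evidence than it appears.

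**Working it through.** **No planned figure to reproduce.** The documents give no FOSI-18 sample size, event count, standard deviation, expected shift or rate of missing baselines. Every size below rests on assumed inputs.

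**Step 1: when Cycle 2 Day 1 is used.**
- A screening score is on or before randomization, so the baseline is not missing.
- With no screening score but a Cycle 1 Day 1 score, the latter lies at most 3 days from randomization. Cycle 2 Day 1 lies about 28 to 31 days away (28 plus 0 to 3), so Cycle 1 Day 1 is chosen, and it is pre-dose.
- With neither, Cycle 2 Day 1 is chosen.

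**Step 2: the main analysis.** A patient censored at time zero enters no risk set and adds nothing to observed or expected events in the log-rank test. The confirmatory DRS-P and total-score tests therefore cannot be changed by the substitution.

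**Step 3: effect on one affected patient.** Assume a 2-point fall by Cycle 2 that persists, and a change score with SD 4. The chance of meeting the 4-point criterion at a given visit is 1 − Φ((4 − μ)/4).
- From a pre-dose baseline, μ = 2: 1 − Φ(0.5) = 0.309.
- From a Cycle 2 Day 1 baseline, μ = 0: 1 − Φ(1) = 0.159.

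The chance roughly halves, but only in patients with that baseline.

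**Step 4: effect on the whole analysis.** Time to a 4-point DRS-P fall was simulated.
- From the documents: 2:1 allocation, the 4-point threshold and 28-day visit spacing.
- Assumed: true score mean 28, SD 4.5, capped at 36; within-patient SD 2; mean drift −0.15 per cycle (between-patient SD 0.3); 12 visits; no dropout; missingness unrelated to arm; 400,000 patients per run.
- Estimator: Σ(d₁r₀/n) ÷ Σ(d₀r₁/n) over visits, with d events, r at risk, n = r₁ + r₀, and 1 = rucaparib.
- A transient shift acts at the first two post-baseline visits only.

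Hazard ratio for worsening (rucaparib/placebo), by share of patients with a Cycle 2 Day 1 baseline:

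| Early fall on rucaparib | 0% | 2% | 5% | 10% | 20% |
|---|---|---|---|---|---|
| None | 1.00 | 1.00 | 1.00 | 1.00 | 0.99 |
| Persistent, 1 point | 1.42 | 1.42 | 1.39 | 1.38 | 1.33 |
| Persistent, 2 points | 1.99 | 1.97 | 1.93 | 1.86 | 1.74 |
| Persistent, 3 points | 2.71 | 2.63 | 2.54 | 2.41 | 2.16 |
| Transient, 1 point | 1.14 | 1.13 | 1.11 | 1.09 | 1.05 |
| Transient, 2 points | 1.36 | 1.33 | 1.30 | 1.25 | 1.16 |
| Transient, 3 points | 1.68 | 1.65 | 1.59 | 1.49 | 1.33 |

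The no-shift runs vary between 0.993 and 1.007, so differences below about 0.01 are simulation noise.

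**Step 5: reading the table.** At 20% affected, a persistent 2-point shift takes the log hazard ratio from ln 1.989 = 0.688 to ln 1.740 = 0.554, a loss of 19%. The transient 2-point shift takes it from ln 1.357 = 0.305 to ln 1.163 = 0.151, a loss of 51%. The transient case loses more because affected patients recover from a lowered baseline. If every patient had a Cycle 2 Day 1 baseline, the ratio would be 0.54 in that case, against 1.02 in the persistent one. Within the range up to 20%, no ratio with an early shift fell below 1.

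**Step 6: pre-dose scores only.** No treatment effect can enter the baseline, so this bias is zero by construction and the 0% column applies.

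**The case against.** The strongest reply is that the rule largely protects itself. It takes the nearest score, so a pre-dose Cycle 1 Day 1 value always comes before Cycle 2 Day 1. SAP section 3 anchors baseline to randomization, whereas Protocol 11.2.1 anchors it to the first day of study drug. One proper use of the rule is therefore to recover Cycle 1 Day 1 scores taken shortly after randomization. The imputation is also labelled supportive. Both replies stand: they limit the reach of the problem, though they do not make Cycle 2 Day 1 a valid baseline.

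A reader might infer more than the documents support:
- **That the rule favours rucaparib outright.** This needs an early fall relative to placebo, and no FOSI-18 data are given. Protocol 3.3.2.1.1 and 3.3.2.1.2 describe early onset only for ALT/AST elevations. The symptomatic events are listed without timing, apart from one dose-limiting nausea in Cycle 1, and come from uncontrolled studies.
- **That only the rucaparib arm is affected.** The rule applies to both arms, and placebo change by Cycle 2 is absorbed too. Only the difference matters. Missing pre-dose scores arise before treatment, so there is no evident reason for their frequency to differ by arm.
- **That an early fall can never lead to an event.** A further fall of the required size still counts.
- **That the no-imputation convention in SAP section 3 shows bias.** It shows a general rule and a specific exception whose wording should be reconciled.

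**Conclusion.** The point holds as a minor one. SAP 11.2 lets an on-treatment score serve as baseline in the supportive FOSI-18 analyses, and this biases the worsening hazard ratio towards rucaparib if rucaparib lowers early scores relative to placebo. Under the assumed persistent 2-point shift, the movement is at most 0.06 on the hazard ratio with up to 5% of patients affected (1.99 to 1.93) and 0.25 with 20% affected (1.99 to 1.74). Larger or transient shifts change these figures as tabulated, and no early shift means no bias. The true share affected is unknown; since both earlier scores must be missing, it may well be small.

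A reader might conclude that the key patient-reported result is compromised. It is not: the step-down tests do not use imputed baselines, so this rule cannot produce a false confirmatory claim. Nor is the supportive analysis worthless when few patients are affected. Its value as a robustness check depends on a count that the plan does not ask to be reported.

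**What to change.** Change the sentence in SAP 11.2 so that only assessments completed before the first dose (screening or pre-dose Cycle 1 Day 1) may substitute for a missing FOSI-18 baseline. Handle patients with no pre-dose score as in the main analysis, censored at randomization. In the same edit, note in SAP section 3 that 11.2 is an exception to the no-imputation convention, and reconcile the SAP and protocol definitions of baseline.

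The cost is one sentence and the loss of a few patients from a supportive analysis; everyone with a Cycle 1 Day 1 score stays in.

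Protocol 11.3 indicates that endpoints were already summarized when the primary endpoint was unblinded. If this analysis has been run, report the number of patients per arm whose baseline was Cycle 2 Day 1 and repeat the analysis without them.
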